6.2 Nonserious Adverse Events

A *nonserious adverse event* is an AE not classified as serious.

6.2.1 Nonserious Adverse Event Collection and Reporting

The collection of nonserious AE information should begin at initiation of study drug. Nonserious AE information should also be collected from the start of a placebo lead-in period or other observational period intended to establish a baseline status for the participants. All nonserious adverse events (not only those deemed treatment-related) are to be collected continuously during the treatment period and for a minimum of 100 days following the last dose of study treatment.

Nonserious AEs should be followed to resolution or stabilization, or reported as SAEs if they become serious (see [Section 6.1.1](#)). Follow-up is also required for nonserious AEs that cause interruption or discontinuation of study drug and for those present at the end of study treatment as appropriate. All identified nonserious AEs must be recorded and described on the nonserious AE page of the CRF (paper or electronic).

Completion of supplemental CRFs may be requested for AEs and/or laboratory abnormalities that are reported/identified during the course of the study.

6.3 Laboratory Test Result Abnormalities

The following laboratory test result abnormalities should be captured on the nonserious AE CRF page or SAE Report Form (electronic) as appropriate. Paper forms are only intended as a back-up option when the electronic system is not functioning.

- Any laboratory test result that is clinically significant or meets the definition of an SAE
- Any laboratory test result abnormality that required the participant to have study drug discontinued or interrupted
- Any laboratory test result abnormality that required the participant to receive specific corrective therapy

It is expected that wherever possible, the clinical rather than laboratory term would be used by the reporting investigator (eg, anemia versus low hemoglobin value).

6.4 Pregnancy

If, following initiation of the study drug, it is subsequently discovered that a study participant is pregnant or may have been pregnant at the time of study exposure, including during at least 5 half-lives after product administration, the investigator must immediately notify the BMS Medical Monitor/designee of this event and complete and forward a Pregnancy Surveillance Form to BMS Designee within 24 hours of awareness of the event and in accordance with SAE reporting procedures described in [Section 6.1.1](#).

In most cases, the study drug will be permanently discontinued in an appropriate manner (eg, dose tapering if necessary for participant safety). Please call the BMS Medical Monitor within 24 hours of awareness of the pregnancy.

In the rare event that the benefit of continuing study drug is thought to outweigh the risk, after consultation with BMS, the pregnant participant may continue study drug after a thorough discussion of benefits and risk with the participant, if allowed by local regulations.

Protocol-required procedures for study discontinuation and follow-up must be performed on the participant unless contraindicated by pregnancy (eg, x-ray studies). Other appropriate pregnancy follow-up procedures should be considered if indicated.

The investigator must immediately notify the BMS (or designee) Medical Monitor of this event and complete and forward a Pregnancy Surveillance Form to BMS (or designee) within 24 hours of awareness of the event and in accordance with SAE reporting procedures described in [Section 6.1.1](#).

Follow-up information regarding the course of the pregnancy, including perinatal and neonatal outcome and, where applicable, offspring information must be reported on the Pregnancy Surveillance Form.

Any pregnancy that occurs in a female partner of a male study participant should be reported to BMS. Information on this pregnancy will be collected on the Pregnancy Surveillance Form.

6.5 Overdose

An overdose is defined as the accidental or intentional administration of any dose of a product that is considered both excessive and medically important. Overdose, as a verbatim term (as reported by the investigator), should not be reported as an AE/SAE unless it is an intentional overdose taken with possible suicidal/self-harming intent. Such overdoses should be reported regardless of sequelae and should specify "intentional overdose" as the verbatim term.

All instances of accidental overdose and/or dosing errors should be reported on the Dosage Administration Record CRF. (see [Section 6.1.1](#) for reporting details.).

6.6 Potential Drug Induced Liver Injury (DILI)

Wherever possible, timely confirmation of initial liver-related laboratory abnormalities should occur prior to the reporting of a potential DILI event. All occurrences of potential DILIs, meeting the defined criteria, must be reported as SAEs (see Section 6.1.1 for reporting details).

Potential drug induced liver injury is defined as:

1. AT (ALT or AST) elevation > 3 times upper limit of normal (ULN)
AND
2. Total bilirubin > 2 times ULN, without initial findings of cholestasis (elevated serum alkaline phosphatase),
AND
3. No other immediately apparent possible causes of AT elevation and hyperbilirubinemia, including, but not limited to, viral hepatitis, pre-existing chronic or acute liver disease, or the administration of other drug(s) known to be hepatotoxic.

6.7 Other Safety Considerations

Any significant worsening noted during interim or final physical examinations, electrocardiogram, x-ray filming, any other potential safety assessment required or not required by protocol should also be recorded as a nonserious or serious AE, as appropriate, and reported accordingly.

6.7.1 Adverse Events of Interest

Definition of immune-mediated adverse events (IMAEs)

Immune-mediated AEs are specific events (that include pneumonitis, diarrhea/colitis, hepatitis, nephritis/renal dysfunction, rash, and endocrine [adrenal insufficiency, hypothyroidism/thyroiditis, hyperthyroidism, diabetes mellitus, and hypophysitis]) for which participants received immunosuppressive medication for treatment of the event, with the exception of endocrine events (hypothyroidism/thyroiditis, hyperthyroidism, hypophysitis, diabetes mellitus, adrenal insufficiency), which are included regardless of treatment since these events are often managed without immunosuppression.

IMAEs include events, regardless of causality, occurring within 100 days of the last dose.

Table 6.7.1-1 below provides a summary of the IMAEs category and their respective PTs. This list is participant to change based on Health Authority feedback or change of MedDRA version. The final list used will be described in the CSR.

Table 6.7.1-1: Preferred Terms Included in Analysis of IMAEs to Support Warnings and Precautions

IMAE Category	PTs included under IMAE Category
Pneumonitis	Pneumonitis, Interstitial lung disease
Diarrhea/Colitis	Diarrhea, Colitis, Enterocolitis

Table 6.7.1-1: Preferred Terms Included in Analysis of IMAEs to Support Warnings and Precautions

IMAE Category	PTs included under IMAE Category
Hepatitis	Hepatotoxicity, Hepatitis, Hepatitis acute, Autoimmune hepatitis, AST increased, ALT increased, Bilirubin increased, ALP increased
Adrenal insufficiency	Adrenal insufficiency
Hypothyroidism/Thyroiditis	Hypothyroidism, Thyroiditis Thyroiditis acute (collapsed with thyroiditis for frequency), Autoimmune thyroiditis (collapsed with thyroiditis for frequency)
Hyperthyroidism	Hyperthyroidism
Hypophysitis	Hypophysitis
Diabetes mellitus	Diabetes mellitus, Diabetic ketoacidosis
Nephritis and renal dysfunction	Nephritis, Nephritis allergic, Tubulointerstitial nephritis, Acute renal failure, Renal failure, Increased creatinine
Rash	Rash, Rash maculopapular

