1.5 Product Development Background

Nivolumab (Opdivo) is in clinical development for the treatment of patients with melanoma, non-small cell lung cancer (NSCLC), renal cell carcinoma (RCC), head and neck carcinoma and other tumors (eg, gastric cancer, glioblastoma multiforme, Hodgkins lymphoma, small cell lung cancer). Opdivo as monotherapy has been approved in the US in multiple indications, including, unresectable or metastatic melanoma and disease progression following ipilimumab and a BRAF inhibitor, if BRAF V600 mutation positive; previously untreated patients with BRAF wild-type unresectable or metastatic melanoma; NSCLC with progression on or after platinum-based chemotherapy; and advanced renal cell carcinoma who have received prior anti-angiogenic therapy. The combination of nivolumab and ipilimumab has also been approved in the US for the treatment of previously untreated metastatic melanoma.

Patients with recurrent or metastatic SCCHN have poor prognosis and experience limited survival benefit with standard of care therapies. In patients with recurrent or metastatic SCCHN who progress with platinum chemotherapy, nivolumab demonstrated prolonged survival benefit over standard of care in the Checkmate 141 study and is poised to become the standard of care in this population. To further improve clinical outcomes in patients with recurrent or metastatic SCCHN in the first-line treatment setting, nivolumab in combination with ipilimumab is being explored in the CA209651 clinical study.

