#### • Post baseline period:

- On-treatment AEs will be defined as AEs with an onset date and time on or after the date and time of the first dose of study treatment (or with an onset date on or after the day of first dose of study treatment if time is not collected or is missing). For subjects who are off study treatment, AEs will be included if event occurred within a safety window of 100 days after the last dose of study treatment. No "subtracting rule" will be applied when an AE occurs both pre-treatment and post-treatment with the same preferred term and grade.
- On-treatment evaluations (laboratory tests, pulse oximetry and vital signs) will be defined as evaluations taken after the day (and time, if collected and not missing) of first dose of study treatment. For subjects who are off study treatment, evaluations should be within a safety window of 100 days after the last dose of study treatment.

 Late-emergent drug-related AEs will be defined as drug-related AEs with an onset date greater than 100 days after the last dose of study treatment in subjects who are off study treatment.

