# 7.1.1.3 Immune-Mediated Adverse Events (US Submission)

In order to further characterize AEs of special clinical interest, analysis of immune-mediated AEs (IMAE) will be conducted. IMAEs are specific events (or groups of PTs describing specific events) that include pneumonitis, diarrhea/colitis, hepatitis, nephritis/renal dysfunction, rash, endocrine (adrenal insufficiency, hypothyroidism/thyroiditis, hyperthyroidism, diabetes mellitus, and hypophysitis), and other specific events, considered as potential immune-mediated events by investigator that meet the definition summarized below:

- those occurring within 100 days of the last dose,
- regardless of causality,
- treated with immune-modulating medication (of note, endocrine AEs such as adrenal insufficiency, hypothyroidism/thyroiditis, hyperthyroidism, diabetes mellitus, and hypophysitis are considered IMAEs regardless of immune-modulating medication use, since endocrine drug reactions are often managed without immune-modulating medication).
- with no clear alternate etiology based on investigator assessment, or with an immune-mediated component

The list of MedDRA preferred terms used to identify IMAEs is revisited quarterly and updated accordingly. The preferred terms used for the selection at the time of the database lock by categories will be provided.

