# 7.6 Safety

All figures and summary tables for safety will be produced on the "all treated PD-L1 CPS  $\geq$  20," and "all treated" populations. Safety listings will be done on the all treated populations but will have variables for PD-L1 CPS added to them.

Analyses in this section will be tabulated by treatment group as treated, unless otherwise specified.

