# 7.6.7 Immune-Mediated Adverse Events (US Submission)

IMAEs will be summarized by treatment group for each immune-mediated category / PT using the 100-day safety window:

- Overall summary of non-endocrine IMAEs by worst CTC grade (any grade, grade 3-4, grade 5) where immune modulating medication was initiated presented by Category / PT.
- Overall summary of endocrine IMAEs by worst CTC grade (any grade, grade 3-4, grade 5) presented by Category / PT.
- Overall summary of non-endocrine IMAEs leading to discontinuation by worst CTC grade (any grade, grade 3-4, grade 5) where immune modulating medication was initiated presented by Category / PT.
- Overall summary of endocrine IMAEs leading to discontinuation by worst CTC grade (any grade, grade 3-4, grade 5) presented by Category / PT.
- Overall summary of non-endocrine IMAEs leading to dose delay or reduction by worst CTC grade (any grade, grade 3-4, grade 5) where immune modulating medication was initiated presented by Category / PT
- Overall summary of endocrine IMAEs leading to dose delay or reduction by worst CTC grade (any grade, grade 3-4, grade 5) presented by Category / PT.
- Summaries of time-to onset and time-to resolution of non-endocrine IMAEs where immune modulating medication was initiated presented by Category.
- Summaries of time-to onset and time-to resolution of endocrine IMAEs presented by Category.

A by-subject listing of IMAEs will be provided. By-subject listings of time-to resolution for longest IMAEs cluster (any grade and grade 3-5 in separate summaries) will also be provided. For new studies which collect investigator assessment of potential IMAE data, a by-subject listing of AEs considered as immune-mediated events per investigator but not qualified for IMAEs definition will also be provided.

In addition, for all nivolumab treated subjects who experienced at least one IMAE, the following data presentation will be provided:

- Summary of subjects who were re-challenged with nivolumab by IMAE category, with extended follow-up
- Summary of subjects who were re-challenged with nivolumab or ipilimumab by IMAE category, with extended follow-up

For these, re-challenge is considered to have occurred when last nivolumab and/or ipilimumab infusion was administered after the onset of an IMAE.

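### The 100-day IMAE window does not stop at subsequent therapy, so immune events from a next-line checkpoint inhibitor can be tabulated under EXTREME

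*Protocol*

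**What the plan says.** Protocol 6.7.1 sets the rule: "IMAEs include events, regardless of causality, occurring within 100 days of the last dose". Non-endocrine events count only if immunosuppressive medication was given for them. Endocrine events count regardless of treatment.

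SAP 7.1.1.3 repeats the window ("those occurring within 100 days of the last dose"), again disregards causality, and again requires non-endocrine events to be "treated with immune-modulating medication". It then adds a condition that the protocol lacks: "with no clear alternate etiology based on investigator assessment, or with an immune-mediated component".

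For reporting, SAP 7.6.7 says that "IMAEs will be summarized by treatment group for each immune-mediated category / PT using the 100-day safety window". The grouping comes from SAP 7.6: "Analyses in this section will be tabulated by treatment group as treated, unless otherwise specified". The general rule for the post-baseline period in SAP 6.1 has the same end point: "AEs will be included if event occurred within a safety window of 100 days after the last dose of study treatment".

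None of these sections mentions the start of subsequent anti-cancer therapy. On what control participants may receive next, Protocol 1.5 says that nivolumab after platinum progression "is poised to become the standard of care in this population".

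**The concern.** Arm B participants receive no checkpoint inhibitor on study, so their IMAE rate should describe the background against which nivolumab plus ipilimumab is read. Many will stop at progression on a platinum-based regimen, which is the setting in which the protocol expects nivolumab to become standard. If a PD-1 inhibitor is started within 100 days of the last study dose, an immune event that it causes falls inside the window and is reported under EXTREME. That can raise the control rate and may make the added immune toxicity of the experimental arm look smaller than it is.

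The IMAE tables are among the most open to this, because they disregard causality and use only the 100-day window. Endocrine IMAEs are the most exposed, since they need no immune-modulating treatment to qualify. Time to onset of IMAEs (SAP 7.6.7 and Appendix 1) runs from the first study dose, so an event after a switch would also enter there as a late onset. No planned IMAE summary would show a reader how many events followed a switch.

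**Working it through.** The plan states no figure on this point, so there is none to reproduce. The check is a reading of the rules, a timing check and an illustrative calculation.

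**Tracing one event through the rules.** Take an Arm B participant who progresses, starts a PD-1 inhibitor, and develops hypothyroidism within 100 days of the last cetuximab dose.

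- Window: met under both documents.
- Causality: disregarded under both.
- Treatment of the event: not required, because it is endocrine.
- Etiology: the protocol has no such condition, so the event counts. In the SAP, the investigator may name the next-line drug as a clear alternate cause, which fails the first branch. The second branch asks only for an immune-mediated component, which a PD-1-induced event has. The SAP does not say how the two branches interact after a switch.
- Arm: as treated with study regimen, so EXTREME.

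The event counts under the protocol and is not clearly excluded under the SAP.

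**Would it be recorded?** Protocol 3.1 and 6.2.1 collect all adverse events for at least 100 days after the last dose. Follow-up visit 2 falls at about 30 + 90 = day 120 (day 106 to 134 with both visit windows). The whole window is observed.

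**Illustrative size.** Added Arm B incidence = f × q × (1 − pC), where

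- f = share of Arm B starting a PD-1 inhibitor within 100 days of last dose (assumed 10–50%);
- q = chance of a qualifying IMAE before day 100 once started (assumed 2–19%);
- pC = Arm B IMAE incidence without next-line events, and pE = the Arm A incidence (both assumed).

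Two placeholders are borrowed from Protocol Table 1.2.3-1 (first-line NSCLC). There, 10/52 = 19% had grade 3–4 drug-related events on nivolumab alone, and 11/39 = 28% on the study's combination schedule. Neither is an IMAE rate. Using 19% for q applies a full-exposure rate to part of a 100-day window, so it is an extreme.

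| pE, pC | f, q | Added to Arm B (points) | Difference without it → as tabulated (points) |
|---|---|---|---|
| 28%, 5% | 10%, 2% | 0.10 × 0.02 × 0.95 = 0.19 | 23 → 22.81 |
| 28%, 5% | 30%, 5% | 0.30 × 0.05 × 0.95 = 1.425 | 23 → 21.575 |
| 28%, 5% | 50%, 19% | 0.50 × 0.19 × 0.95 = 9.025 | 23 → 13.975 |
| 40%, 10% | 10%, 2% | 0.10 × 0.02 × 0.90 = 0.18 | 30 → 29.82 |
| 40%, 10% | 30%, 5% | 0.30 × 0.05 × 0.90 = 1.35 | 30 → 28.65 |
| 40%, 10% | 50%, 19% | 0.50 × 0.19 × 0.90 = 8.55 | 30 → 21.45 |

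**Possible offset in Arm A.** The same open window applies there. If 30% of Arm A started next-line chemotherapy or cetuximab in the window and 5% of those had a qualifying listed event, Arm A would gain 0.30 × 0.05 × 0.72 = 1.08 points. At 10% it would gain 0.30 × 0.10 × 0.72 = 2.16 points. Combined with the middle case for Arm B, the tabulated difference would be 23 − 1.425 + 1.08 = 22.655 or 23 − 1.425 + 2.16 = 23.735. The net direction therefore depends on inputs that the documents do not give.

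**The case against.** The strongest case on the other side has five parts.

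- **Other tables limit the damage.** Drug-related events are summarized with both 30-day and 100-day windows (SAP 7.6.5). Select adverse events use 30 days and include drug-related versions (SAP 7.6.6). Serious events, discontinuations and dose modifications use 30 days. SAP 7.6.8 plans a drug-related OEOSI table beside the all-causality one. This stands. A reader might infer that the IMAE tables are the main account of added immune risk, or that safety reporting in general is affected; the documents support neither. The exposure is confined to 100-day analyses that disregard causality.
- **The etiology criterion may screen events out.** It may remove some, if investigators treat the next-line drug as a clear alternate cause. It is not a reliable guard, because of its second branch. The text supports saying that such events are not clearly excluded. It does not support saying that they will all be counted.
- **Arm A can gain events too.** Protocol Table 6.7.1-1 lists diarrhea, rash, liver test increases, renal failure and raised creatinine. Protocol 4.5.3.2 treats rash, diarrhea, nephrotoxicity and raised bilirubin as toxicities of EXTREME drugs. Since non-endocrine terms need immune-modulating treatment to qualify, I expect the offset to be limited, but this is judgment.
- **Cutting the main table at subsequent immunotherapy alone would be differential.** It would remove mainly Arm B events and leave Arm A events from next-line chemotherapy in place. This stands, and it is why the change below is supportive and cut at any subsequent systemic therapy.
- **The listings allow recovery.** By-subject listings of IMAEs and of subsequent therapy are planned (SAP 7.6.7 and 7.4.3.2). A reader with both could identify events after a switch, but the summary tables would not show them.

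**Conclusion.** The gap is real. Neither document ends the 100-day, causality-blind IMAE window at subsequent anti-cancer therapy, and the SAP etiology criterion does not clearly exclude events due to a next-line checkpoint inhibitor. Such events in Arm B can be tabulated as control-arm IMAEs and may understate the between-arm difference. The all-causality OEOSI table is exposed in the same way.

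A reader might go further and conclude that the IMAE contrast is in fact shrunk. The documents do not show that: they give no rate or timing of next-line checkpoint-inhibitor use and no IMAE rates. The illustrated addition to Arm B of 0.2 to 9.0 points (about 1.4 at f = 30%, q = 5%) rests entirely on assumed inputs, its top is an extreme, and it ignores any offset in Arm A.

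The IMAE analyses are descriptive and no hypothesis test is affected. This is a modest weakness with an inexpensive remedy.

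**What to change.** - In SAP 7.6.7, keep the planned 100-day IMAE table. Add a supportive IMAE summary that counts events to the earlier of 100 days after last dose and the day before the start of any subsequent systemic anti-cancer therapy. A further version cut only at subsequent immunotherapy can be added if wanted.
- Report by arm the number of IMAEs with onset on or after that start.
- Do the same for the all-causality OEOSI table in SAP 7.6.8.
- Align the IMAE definitions in Protocol 6.7.1 and SAP 7.1.1.3, including whether the etiology criterion applies and how its two branches work once another therapy has begun.

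The cost is one or two extra tables and one date condition. Protocol Table 5.1-3 already has subsequent cancer therapy documented during follow-up, and the SAP uses its start date to censor PFS (4.2.2.1) and DOR (4.2.4). The downside is small: some late study-drug events in participants who switch therapy drop out of the truncated summary, but they stay in the planned table.

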7 DATA MONITORING COMMITTEE AND OTHER EXTERNAL COMMITTEES

A Data Monitoring Committee (DMC) will be utilized to provide general oversight and safety considerations for this study. The DMC will provide advice to the Sponsor regarding actions the committee deems necessary for the continuing protection of participants enrolled in this study. The DMC will be charged with assessing such actions in light of an acceptable risk/benefit profile for nivolumab. The DMC will act in an advisory capacity to BMS and will monitor participant safety data for the study.

The DMC will be advisory to the clinical study leadership team. The clinical study leadership will have responsibility for overall conduct of the study including managing the communication of study data. The group will be responsible for promptly reviewing the DMC recommendations, for providing guidance regarding the continuation or termination of the study, and for determining whether amendments to the protocol or changes to the study conduct are required.

Details of the DMC responsibilities and procedures will be specified in the DMC charter.

